4.6 INTERIM ANALYSES

No efficacy interim analyses were performed in this study.

Appendix 1

Endpoint Details

ADAS-Cog 13

The item scores for individual items are derived from the following:

- Item 1 - Word recall: Three trials of reading and recall are given. The item score is calculated using the mean number of “total not recalled” recorded on the electronic system for the three trials. The item score ranges from 0 to 10. If the “total not recalled” in any of the three trials is missing, then the item score will be set to missing.
- Items 2 - Following commands: The item score is the number of incorrect responses on commands (i.e., no) for Questions 2a–e on the electronic system. The score ranges from 0 to 5.
- Items 3 - Constructional praxis: The item score is the number of incorrect drawings (i.e., Drawn correct? = no) for Questions 3a–d on the electronic system. The score ranges from 0 to 5 as follows:

0 = All 4 drawings correct
1 = 1 form drawn incorrectly
2 = 2 forms drawn incorrectly
3 = 3 forms drawn incorrectly
4 = 4 forms drawn incorrectly
5 = No figures drawn, scribbles; parts of forms; words instead of forms

- Items 4 - Delayed word-recall task: The item score is “total not recalled” on the electronic system. The score ranges from 0 to 10.
- Item 5: Naming objects and fingers: The item score is derived on the basis of “total incorrect” recorded on the electronic system and determined as follows:

0 = 0 to 2 incorrect
1 = 3 to 5 incorrect
2 = 6 to 8 incorrect
3 = 9 to 11 incorrect
4 = 12 to 14 incorrect
5 = 15 to 17 incorrect

- Item 6 - Ideational praxis: The item score equals the “total incorrect” recorded on the electronic system for this item. The score ranges from 0 to 5.
- Item 7 – Orientation: The item score equals “total incorrect” recorded on the electronic system for this item. The score ranges from 0 to 8.
- Item 8 - Word recognition: The item score equals “total incorrect” recorded on the electronic system when “total incorrect” is ≤ 12 and is 12 if “total incorrect” is > 12 . The item score ranges from 0 to 12.
- Item 9 - Remembering test instructions: The item score is derived on the basis of replies recorded on the electronic system and determined as follows:

0 = None
 1 = Very mild
 2 = Mild
 3 = Moderate
 4 = Moderately severe
 5 = Severe.

- Item 10 - Comprehension: The item score is derived on the basis of replies recorded on the electronic system and determined as in Item 9.
- Item 11 - Word finding difficulty: The item score is derived on the basis of replies recorded on the electronic system and determined as in Item 9.
- Item 12 - Spoken language ability: The item score is derived on the basis of replies recorded on the electronic system and determined as in Item 9.
- Item 13 - Number cancellation: The cancellation score equals the number of target hits (minus) the number of errors (minus) number of times reminded of task, for which:

0 = Cancellation score > 23
 1 = Cancellation scores 18–22
 2 = Cancellation scores 13–17
 3 = Cancellation scores 9–12
 4 = Cancellation scores 5–8
 5 = Cancellation scores ≤ 4

CDR GS

The global CDR is derived from the scores in each of the six categories (“box scores”) as follows:

- a) CDR-global score = M if at least three secondary categories are given the same scores as memory.
- b) If at least three secondary categories are on one side of M, then CDR-global score = score of these secondary categories. Except in the case of c.
- c) CDR-global score = M when three secondary categories are scored greater than M and two secondary categories are scored less than M, or vice versa.
- d) If $M = 0.5$, CDR-global score cannot be 0, it can only be 0.5 or 1. CDR-global score = 1 if at least three of the other categories are scored ≥ 1 .
- e) If $M = 0$, CDR-global score = 0, unless there is impairment (≥ 0.5) in two or more secondary categories, in which case, CDR-global score = 0.5.
- f) If there are ties in the secondary categories on either side of M, choose the tied scores closest to M for the CDR-global score. (For example, if M and another secondary category = 3, two secondary categories = 2 and two secondary categories = 1 then CDR-global score = 2).
- g) When only one or two secondary categories are given the same score as M, CDR-global score = M, as long as no more than two secondary categories are on either side of M.
- h) When $M \geq 1$, the CDR-global score cannot be 0. In such a circumstance, CDR-global score = 0.5 when the majority of secondary categories are 0.

STATISTICAL ANALYSIS PLAN

STUDY TITLE: A PHASE III, RANDOMIZED, DOUBLE-BLIND, PLACEBO-CONTROLLED, PARALLEL-GROUP, MULTICENTER, EFFICACY AND SAFETY STUDY OF GANTENERUMAB IN PATIENTS WITH MILD ALZHEIMER'S DISEASE; PART II: OPEN-LABEL EXTENSION FOR PARTICIPATING PATIENTS

STUDY NUMBER: WN28745
VERSION NUMBER: 1
ROCHE COMPOUND(S): Gantenerumab (RO4909832)
EUDRACT NUMBER: 2013-0033990-95
IND NUMBER: 102266

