6.1.7 Subgroup Analyses

Since this is a global study, the effect of some demographic variables and baseline characteristic such as race and region on efficacy and safety will be summarized within subgroups using descriptive statistics (please see subgroups below). Additional exploratory analyses of efficacy results may be performed using an MMRM model, with the subgroup, a treatment-by-subgroup interaction term, and a subgroup-by-time interaction terms included along the independent effects described above. This

exploratory subgroup analysis may be important in understanding the effect of these variables on efficacy and safety. Such exploratory analyses will be performed primarily in the case where the descriptive statistics results indicate substantial differences between the subgroups.

The following variables will be used to define the subgroups for these analyses:

- Sex
- Age
- Race
- APOE ϵ 4 status
- Fc γ receptor genotype
- Region

Additional subgroup analyses may be performed with subgroups defined based on baseline levels of CSF t-tau, p-tau, t-tau to A β 1–42 ratio, and p-tau to A β 1–42 ratio.

Since Part 1 (i.e., the double-blind period) has been suspended and replaced by an OLE, the primary and key secondary efficacy analyses will not be performed. However, exploratory and descriptive analyses will be conducted at the end of Part 1.

6.2 ANALYSES IN PART 2

As Part 2 is an OLE, regular safety analyses will be conducted as described in Section 6.1.4. In addition, descriptive statistics and changes from baseline will be used to explore clinical findings (including efficacy, global functioning, and biomarkers). PK analysis will be conducted according to Section 6.1.5.

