2.3 OUTCOME MEASURES

For all questionnaire-based outcome measures, scores from the electronic capture system (ie. Bracket tablet) should be used wherever possible.

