2.3.1.1 Alzheimer's Disease Assessment Scale–cognition (13 item sub-scale)

ADAS-Cog is a cognitive assessment designed to measure the severity of some of the most important symptoms of AD, including impairment of memory and language. The 13-item total score is calculated using the sum of all the 13 item scores (see Appendix 1 for more information). This scale is administered electronically and if any item score is missing or is invalid, the total score will be set to missing. The 13-item ADAS-cog total score ranges from 0 to 85. Higher scores indicate greater impairment.

2.3.1.2 Alzheimer's Disease Cooperative Study – Activities of Daily Living (ADCS-ADL).

The ADCS-ADL is the scale most widely used to assess functional outcome in patients with AD. The ADCS-ADL covers both basic ADL (e.g., eating and toileting) and more

complex ADL or instrumental ADL (e.g., using the telephone, managing finances, preparing a meal). The ADCS-ADL consists of 32 items (questions and sub-questions) each with multiple choice answers. For example, questions with three possible responses often have the following response structure (3 points = without supervision or help, 2 points = with supervision, 1 point = with physical help). Total score is calculated by summing all sub-scores. The ADCS-ADL total score ranges from 0 - 78 with lower values indicating greater impairment. The basic ADL (bADL) score is calculated by summing questions 1 to 5 and 6b inclusive. The instrumental ADL (iADL) score is calculated by summing questions 6a and 7 to 23 inclusive. This scale is administered electronically with no option to miss a question. Therefore, missing data will only be present if the entire scale is missing. However, due to a translation error in Spanish for Spain, question 18 will be set to missing for all patients from Spain. This will allow the bADL score to be calculated but the iADL and total scores will be missing for these patients.

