4. STATISTICAL METHODS

In the following sections, for all continuous variables for which descriptive statistics are indicated, the following statistics will be reported: the number of observations, the mean, median, standard deviation, and minimum and maximum. The 25th and 75th percentiles (Q1 and Q3) will also be reported for selected tables.

In all analysis, baseline is defined as the last available assessment up to and including the first day of study drug intake in the double-blind period (Part 1).

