4.4.1 Primary Efficacy Endpoint

The co-primary efficacy outcome measures are:

- The difference between Gantenerumab and Placebo treated patients in the mean change in ADAS-Cog 13 from baseline (Day 1) to Week 104 in the population of all randomized patients.

- The difference between Gantenerumab and Placebo treated patients in the mean change in ADCS-ADL from baseline (Day 1) to Week 104 in the population of all randomized patients.

For each of the co-primary endpoints, the absolute values, change from baseline and percentage change from baseline will be summarized by time-windowed visit.

In addition, the co-primary endpoints will also be analysed using a mixed model with repeated measures (MMRM). The model will use an unstructured variance – covariance matrix for the repeated measures allowing the inclusion of individuals with incomplete data. The following variables will be included in the modelling:

Dependant variable	ADAS-Cog 13 or ADCS-ADL
Independent variables	Treatment (placebo or Gantenerumab) APOE status (carrier or non-carrier) Baseline ADAS-Cog 13 or ADCS-ADL score Time (weeks relative to first dose in study) Treatment (placebo or Gantenerumab) by time (weeks relative to first dose in study) interaction

Patient, treatment and time will be treated as class variables. All data from all patients (as defined in Section 2.2) will be used, including data from Week 104/early termination visits.

A treatment-by-time interaction contrast will be used to estimate the difference between gantenerumab and placebo in the mean change from baseline at each visit. Least square means, standard errors, 95% confidence intervals will be reported for gantenerumab relative to placebo.

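### The ADAS-Cog13 number-cancellation bands give no item score to a cancellation score of exactly 23, so a complete assessment may lose its total

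*SAP*

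**What the plan says.** Appendix 1 of the Part 1 SAP is the only place in the documents where ADAS-Cog13 item scoring is set out. It introduces the list with "The item scores for individual items are derived from the following". For Item 13 the cancellation score is target hits less errors less reminders. The two best bands are "0 = Cancellation score > 23" and "1 = Cancellation scores 18–22". The others are 13–17 (item score 2), 9–12 (3), 5–8 (4) and 4 or below (5).

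Four other provisions of the Part 1 SAP bear on the point:

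- **Missing items (Section 2.3.1.1):** "if any item score is missing or is invalid, the total score will be set to missing". Section 5.5.1 of the OLE SAP has the same rule but no item mapping.
- **Source of scores (Section 2.3):** "scores from the electronic capture system (ie. Bracket tablet) should be used wherever possible".
- **Baseline (Section 4):** "baseline is defined as the last available assessment up to and including the first day of study drug intake".
- **Analysis (Section 4.4.1):** ADAS-Cog13 is summarised by visit and also fitted with an MMRM that gives least-squares means, standard errors and 95% confidence intervals.

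Protocol Section 4.5.5.1 names number cancellation as one of the added items but gives no scoring for it. Protocol Section 6.1.7 says that, after the conversion to open label, "the primary and key secondary efficacy analyses will not be performed".

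**The concern.** A scoring rule for a co-primary measure should assign exactly one item score to every possible raw result. This one skips a value that a patient can obtain, just below the best band. A programmer who works from Appendix 1 has two options, and neither is satisfactory:

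- **Treat Item 13 as having no valid score.** The missing-item rule then removes the whole total, although all 13 items were completed. The loss depends on performance, because it occurs at a single performance level. After baseline it removes a visit. At baseline, the last-available-assessment rule could bring in the screening total instead, since the Part 1 schedule has ADAS-Cog13 at both screening and baseline.
- **Patch the gap silently.** The plan does not say whether 23 scores 0 or 1, so the derivation cannot be reproduced from it.

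With formal primary testing dropped, the stake is the accuracy and traceability of the reported estimates, not a confirmatory test.

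**Working it through.** **1. Reproduce the stated range.** The item maxima in Appendix 1, for Items 1 to 13 in order, are:

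10 + 5 + 5 + 10 + 5 + 5 + 8 + 12 + 5 + 5 + 5 + 5 + 5 = 85

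This matches the 0 to 85 range in Section 2.3.1.1, so the item list is otherwise complete.

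**2. Test the Item 13 bands.** The score is a count minus two counts, so it is a whole number. Each integer from −60 to 60 was compared with the six bands.

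| Item score | Band as printed | Integers covered |
|---|---|---|
| 0 | > 23 | 24 and above |
| none | – | **23** |
| 1 | 18–22 | 18 to 22 |
| 2 | 13–17 | 13 to 17 |
| 3 | 9–12 | 9 to 12 |
| 4 | 5–8 | 5 to 8 |
| 5 | ≤ 4 | 4 and below |

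The only integer in no band is 23, and no integer falls in two. If the top band is read as 23 or more, every integer falls in exactly one band. Extending the second band to 18–23 also closes the gap. The bands for Item 5, which is scored in a similar way, cover 0 to 17 without a break.

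**3. Is it a text-reading artefact?** Probably not. The ≤ sign in the same list and the ≥ signs in the CDR rules just below it came through correctly.

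**4. How often would 23 occur?** The documents give no distribution. Assume a normal score with mean μ and SD σ:

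P(23) = Φ((23.5 − μ)/σ) − Φ((22.5 − μ)/σ)

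| μ | σ = 5 | σ = 6.5 | σ = 8 |
|---|---|---|---|
| 10 | 0.0027 | 0.0083 | 0.0133 |
| 12 | 0.0071 | 0.0147 | 0.0194 |
| 14 | 0.0158 | 0.0236 | 0.0265 |
| 16 | 0.0300 | 0.0344 | 0.0340 |
| 18 | 0.0484 | 0.0456 | 0.0410 |
| 20 | 0.0666 | 0.0551 | 0.0465 |

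For example, μ = 20 and σ = 5 gives Φ(0.7) − Φ(0.5) = 0.0666. The range over this grid is 0.3% to 6.7%. It is not a ceiling: a mean of 23 with SD 5 gives 0.080.

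**5. Effect of the 0-or-1 choice.** Each affected total moves by 1 point, so an arm mean at a visit moves by P × 1 = 0.003 to 0.067 points. Even if the choice affected one arm only, the top of the grid is 0.0666 / 2.3 = 2.9% of the planned 2.3-point difference.

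**6. Effect of deletion.** If a fraction P of totals is removed at a visit, and information borrowed by the MMRM from other visits is ignored, the standard error rises by √(1/(1 − P)) − 1:

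- P = 0.0027: 0.14%
- P = 0.0666: 3.5%

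**The case against.** The strongest reply is that the loss may never have happened. The scale was captured on a tablet and, by Protocol Section 4.5.6.11, transferred directly to the database. The Part 1 SAP prefers those scores, and its Section 1 leaves dataset and program details to separate documents, where a rule for 23 may exist. A raw 23 is also a legitimate result, and no text calls it invalid. The printed sign is most likely a one-character slip for 23 or more.

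Much of this is fair. It is why the claim is only that a total may be lost. It does not remove the gap, because none of those sections gives the tablet's cut-offs or says that a finished Item 13 score was supplied. Appendix 1 itself turns recorded counts into item scores for other items: Item 5 bands a recorded number incorrect, and Item 8 caps one at 12. Derivation from Appendix 1 is therefore a realistic route.

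The second reply is about size, and it stands. The distribution is assumed, and a higher mean would exceed the range shown (μ = 23, σ = 5 gives 3.5% of 2.3 points, and 4.2% on the standard error). The one-arm case is a deliberate extreme. One mapping applies to both arms, so the treatment difference moves only by the between-arm difference in how often 23 occurs, partly offset by the same rule at baseline. OLE efficacy is descriptive and exploratory.

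**Conclusion.** The concern holds, as a minor point. It is certain that the printed bands omit 23, and no other text supplies a score for it. Read with the missing-item rule, Appendix 1 leaves a complete assessment without a valid Item 13 score, so the rule is wrong as written. Whether any total was actually lost cannot be settled from the documents. Loss requires that Item 13 was derived from Appendix 1, or that the tablet has the same gap.

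The effect is small. If 23 is scored consistently in both arms, the shift in the treatment difference should be close to zero. The ranges in the working rest on the assumed normal distribution with mean 10 to 20 and SD 5 to 8.

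**What to change.** 1. Confirm from the scale's scoring manual and the tablet's scoring specification whether 23 scores 0 (top band 23 or more, which continues the five-point bands 13–17 and 18–22) or 1 (second band 18–23).
2. Correct the line in Appendix 1 of the Part 1 SAP so that the bands cover every whole number.
3. Check the data for any ADAS-Cog13 total that is missing where the cancellation score is 23. Restore any that are found, and rederive baseline if the screening total had been substituted.
4. Preferably, refer from Section 5.5.1 of the OLE SAP to the corrected mapping, since that document has none of its own.

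The cost is one corrected line, one optional cross-reference and one data query. The query would also settle whether any total was lost.

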5.7.9	Analyses of Subgroups of Interest.....	22
5.8	Interim Analyses	22
5.9	Analyses Related to Corona Virus Disease-19.....	22
6.	SUPPORTING DOCUMENTATION.....	22
7.	REFERENCES	22

LIST OF TABLES

Table 1	Up-Titration Schedule for Open-Label Extension.....	10
---------	---	----

LIST OF ABBREVIATIONS AND DEFINITIONS OF TERMS

Abbreviation or Term	Description
AD	Alzheimer's Disease
ADA	anti-drug antibodies
ADAS-Cog	Alzheimer Disease Assessment Scale-Cognition
ADCS-ADL	Alzheimer's Disease Cooperative Study-Activity of Daily Living Scale
ADRDA	Alzheimer's Disease and Related Disorders Association
AE	adverse event
APOE	apolipoprotein E
ARIA-E	amyloid-related imaging abnormality – oedema/effusion
ARIA-H	amyloid-related imaging abnormality – microhaemorrhages and hemosiderin deposits
AUC _{0-τ}	area under plasma concentration time curve
BGTS	Barkhof Grand Total Score
CCOD	clinical cutoff date
CDR	Clinical Dementia Rating Scale
CDR-SB	Clinical Dementia Rating – Sum of Boxes
C _{max}	maximum plasma concentration
C _{min}	minimum plasma concentration
COVID-19	Corona Virus Disease 2019
CSF	cerebrospinal fluid
CSR	Clinical Study Report
C-SSRS	Columbia-Suicide Severity Rating Scale
DB	double blind
MedDRA	Medical Dictionary for Regulatory Activities
MMSE	Mini Mental State Exam
MRI	magnetic resonance imaging
MRI-C	MRI review committee-Charter
OLE	open-label extension
PD	pharmacodynamic(s)
PET	positron emission tomography
PK	pharmacokinetic(s)
PT	preferred term
QTcB	QT corrected using Bazett's formula
QTcF	QT corrected using Fridericia's formula

SAE	serious adverse events
SAP	Statistical Analysis Plan
SE	safety-evaluable
SOC	system organ class
SUVR	standard uptake value ratio

1. INTRODUCTION

This document describes the planned statistical analyses that will be reported in the final Clinical Study Report (CSR) for open-label extension (OLE) treatment of Study WN28745. The corresponding protocol version is Version 5.

Study WN28745 was designed as a double-blind, Phase III study (Part I) investigating the effect of 2 years of treatment with subcutaneous (SC) gantenerumab 225 mg versus placebo every 4 weeks (Q4W) on cognition and function in patients with mild Alzheimer's disease (AD). The protocol for this study was amended to an open label extension (OLE) (Part II) to evaluate the safety and tolerability of SC doses of gantenerumab up to 1200 mg Q4W. Enrolment into the double blind (DB) part of the study was halted in December 2015 after 389 patients had been randomized; however, the patients from this study continued dosing while the decision to transition to OLE was made. Enrolment into the WN28745 OLE started on 03 March 2016 and was closed on 31 July 2017; overall, 230 of 389 patients originally randomized into the study entered the OLE part.

The duration of the OLE was up to 5 years. In addition to the initial 2 years in the OLE part, patients were given the option to continue receiving open-label gantenerumab treatment until the end of 2020. Patients who discontinued study drug at any time during the OLE part, or who completed the first 2 years of OLE only were asked to complete follow-up visits at 4 and 16 weeks from their last dose (Follow-Up 1 and 2 respectively)

The description of layouts for the CSR outputs, the details about the underlying analysis datasets and programs, and the linking of production outputs to sections in the final CSR are not within the scope of this document.

The language used in this Statistical Analysis Plan (SAP) supersedes that in the protocol and protocol synopsis.

1.1 OBJECTIVES AND OUTCOME MEASURES

1.1.1 Objectives

The primary objective of the OLE was to evaluate the safety and tolerability of gantenerumab at doses up to 1200mg every 4 weeks, focusing on physical and neurologic examinations, vital signs, blood safety tests, ECGs, and adverse event (AE) monitoring.

The secondary objectives included the following:

- To evaluate the effect of higher doses of gantenerumab on imaging biomarkers (positron emission tomography [PET] and magnetic resonance imaging [MRI]), cerebrospinal fluid (CSF) biomarkers, and on clinical outcome measures (cognition and function) over time
- To explore gantenerumab pharmacokinetics (PK) at higher doses.

1.1.2 Outcome Measures

The references for the assessments and procedures can be found in the study protocol, Sections 4.5.

1.1.2.1 Efficacy Measures

The clinical and cognitive efficacy measures are exploratory. During the first two years of the OLE, they included:

- Alzheimer Disease Assessment Scale-Cognition (ADAS-Cog13),
- Mini Mental State Exam (MMSE),
- Clinical Dementia Rating Scale (CDR)
- Alzheimer's Disease Cooperative Study-Activity of Daily Living Scale (ADCS-ADL).

Only the MMSE was collected during the subsequent years of the OLE.

1.1.2.2 Biomarker Outcome Measures

The biomarker outcome measures for this study were as follows:

- Change from baseline (DB screening visit) to OLE Week 104 in MRI volumetry, as assessed on structural MRI:
 - Change from baseline in hippocampal volume
 - Change from baseline in whole brain volume
 - Change from baseline in cortical thickness
 - Change from baseline in ventricular volume

Change from baseline (DB screening visit) to OLE Week 104 in functional brain connectivity, as measured by resting state-MRI, was an exploratory biomarker outcome measure, and its analysis will not be covered in this SAP.

- Change in brain amyloid load over time using a florbetapir F18 injection, a PET radioligand selective to β -amyloid
- The analysis of the CSF biomarker will not be covered in this SAP.

